EEG Data Acquisition and Processing. A 32-channel actiCAP will be positioned according to the 10-20 system, with a Brain Products actiCHamp Plus amplifier. Preprocessing and analysis of EEG data will be performed using custom MATLAB scripts and the EEGLAB processing toolbox. EEG will be digitally re-referenced to the average reference, high pass filtered at 1.0 Hz, and epoched from -1 to 2 seconds to accommodate time-frequency analyses. EEG epochs containing amplitudes >100 μV at any scalp electrode with abnormally distributed data will be rejected. All cleaned, epoched data will be loaded into an EEGLAB STUDY mechanism to compute the time-frequency transform using the 'newtimef' 3-cycle wavelet function to yield Time X Frequency spectrograms. Theta (4-8Hz) and beta (13-30Hz) will be extracted from the pre-computed matrices at frontal (Fz) and parietal (Pz) midline electrodes.

E1G Assessments. We will use the same E1G assay and methods as Gordon et al,¹ who showed that variability in urinary E1G reliably identified perimenopausal women for whom *changes* in E1G predicted depression symptom severity. Week-to-week changes in E1G also differentiated women based on the direction of E1G change (i.e., increasing vs. decreasing levels) and symptom severity. The first morning voided urine will be used for measuring E1G, reflecting an integrated measure of overall E1G level from the previous day, and correlating very highly with serum E2 (r= 0.93).⁴0 At the end of each collection week, research staff will retrieve samples (stored in home freezer) and bring to our lab for storage at -80°C. Urinary E1G is not affected by the repeated freezing and thawing of specimens,⁴0 E1G will be assayed using an enzyme immunoassay (Arbor Assays, Ann Arbor, MI), with sensitivity at < 22.5 pg/mL. The specificity is high, with £ 0.1% cross-reactivity with similarly structured compounds, though cross-reactivity with E2 is higher at 5%. Since this research is focused on within person variation and we are using E1G as an indicator of E2 serum levels, any cross reactivity with E2 will not affect interpretability of our findings. The intra-assay variability = 4-6% and the inter-assay variability = 4-7%. Although there is little evidence to date that sensitivity to progesterone is a risk factor for affective impairment in the MT,¹ pregnanediol-3-glucuronide (PDG; a metabolite of progesterone) is assessed simultaneously with E1G and can be used as a covariate in analyses.

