5.1. Numbers of Participants

Number to be screened: N £ 135Number to be enrolled: N = 50

Up to 135 individuals will be screened. Based on our prior experience with perimenopausal women and intervention studies involving transdermal E2, we estimate that 40% will fail the medical screening for TE2 eligibility, and an additional 20% will not be interested in participating.

It will be necessary to enroll 50 perimenopausal women because our prior experience also suggests that 30% (n=15) will not meet eligibility for TE2 upon further screening, yielding about 35 eligible for the randomized, cross-over study. We conservatively account for 15% (n =5) withdrawal following randomization, yielding 30 women who complete the protocol

Since this is a cross-over study design, all enrolled women will receive both the active TE2 condition and the placebo TE2 condition.

Recruitment: Participants will be recruited through the Menopause Clinics at the UNC Hospitals, and through the UNC Center for Women's Mood Disorders. Additionally, participants will be respondents to advertisements in local newspapers, social media, and mass email listservs seeking volunteers for research. To increase minority applicants, physicians who are African American or of other minority ethnic groups will be included as referral resources, and certain ads will particularly request minority volunteers.

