8.3. Aim-Specific Plans

Plans for Aim 1. The objective of Aim 1 is to define baseline relationships between E1G variability, irritability symptom severity and neurophysiological correlates of threat and frustration (e.g., theta, beta, and associated ERPs (continuous)). Linear regression models will predict irritability symptoms and EEG variables from E1G variability (3) and predict irritability symptoms from EEG measures (2).

Plans for Aim 2. The objective of Aim 2 is to determine whether TE2, versus placebo, will beneficially modify EEG variables and reduce irritability symptom severity. Normality assumption will be accessed using studentized residual and extreme outliers will be assessed individually.

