Aim 2a) The two repeated post-treatment EEG measures (theta, beta, ERPs) will be modeled as a function of fixed factors including baseline EEG measures (continuous), Condition status (TE2 or placebo; binary), and order of Condition (binary) in a linear mixed effects model with a random intercept accounting for the within-subject variance. The two-sided Wald test will test the significance of TE2 effects. 2b) Similarly, weekly irritability symptoms (3 weeks/Condition) will be modeled as a function of fixed factors including baseline irritability symptoms (continuous), Condition, and order of Condition in a linear mixed effects model with a random intercept accounting for within-subject variance. Although we hypothesize that E1G variability will predict outcomes in Aim 1 and Condition effects in Aim 2, we will examine E1G levels if analyses do not support variability. In the statistical models described above, all the estimates of treatment effect, along with 95% confidence interval will be reported in the tabulated forms. Whenever multiple testing is used in the analysis described, Benjamini-Hochberg Procedure will be used to adjust for multiple comparison. All the hypothesis tests that yield large p-values will be reported as being inconclusive. To evaluate the robustness of the proposed study, we will perform sensitivity analysis for all the important findings. More specifically, we will repeat all the statistical analysis by excluding some potential outliers that could be influential points. We expect the sensitivity analysis will preserve the direction of original point estimates from full samples. Based on the study design, there will be potential missing data points caused by subject drop-out, and we assume all the missingness will most like to be missing at random (MAR). Since the linear mixed effects model is capable of handling missing values, the analysis plan will not be affected because of missing data.

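### Section 8.3 relies on the mixed model to absorb missing data, but in Aim 2a that model drops any woman without a usable baseline EEG, even when both her treatment EEGs are usable

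*Combined protocol and SAP*

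**What the plan says.** Section 8.3 names drop-out as the source of missing data, assumes it is missing at random, and concludes: "Since the linear mixed effects model is capable of handling missing values, the analysis plan will not be affected because of missing data".

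The Aim 2a model in the same section has "fixed factors including baseline EEG measures (continuous), Condition status (TE2 or placebo; binary), and order of Condition (binary"), with a random intercept per woman. Table 1 in Section 4.3 lists the EEG measures as a primary outcome.

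The baseline EEG comes from one laboratory session at the end of baseline week 4, Visit 4 (Sections 7.1 and 7.4). This precedes the randomized conditions. Under EEG processing, Section 4.3 says that high-amplitude epochs "with abnormally distributed data will be rejected". It sets no minimum number of usable epochs and gives no rule for a session that fails.

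Section 8.1, which applies to all aims, plans a missing-data sensitivity analysis comparing complete-case estimates with estimates after mean imputation. It does not say which variables are imputed.

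On numbers, Section 5.1 says: "We conservatively account for 15% (n =5) withdrawal following randomization, yielding 30 women who complete the protocol". The synopsis expects these 30 women to have complete data.

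**The concern.** A likelihood-based mixed model uses whatever outcomes are observed and is valid when the rest are missing at random. It has no such provision for a fixed covariate. A row with a missing covariate cannot enter the likelihood, and standard software removes it. Baseline EEG has one value per woman, so both of her rows go together.

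Drop-out after baseline does not cause this, because the baseline EEG is then already recorded. The cause would be a missed or technically unusable Visit 4 session, which Section 8.3 does not consider. The sample size allows for withdrawal but not for unusable EEG, so each such baseline would reduce the 30 directly. At stake is the precision of a primary-outcome contrast. There is also the risk that the handling of these women is chosen after the data have been seen.

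**Working it through.** **1. The plan's own count.** Section 5.1: 50 × 0.70 = 35 women eligible for the crossover; 35 × 0.85 = 29.75, or 30 completers. The figure reproduces.

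**2. What the fit does with a missing baseline.** Data were simulated for 30 women with both post-treatment EEGs (60 rows). The baseline was set missing for 4 women, and the Aim 2a model (baseline, Condition, order, random intercept) was fitted. It used 52 of 60 rows: 60 − 4 × 2 = 52. All four women were lost although both their outcomes were present.

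**3. Why baseline is not needed for the contrast.** Write the Aim 2a model for woman *i* in condition *j* as

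y_ij = β0 + β1·B_i + β2·C_ij + β3·O_i + u_i + e_ij,

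with B the baseline EEG, C the Condition, O the order and u the random intercept. For a woman observed in both conditions,

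y_i,TE2 − y_i,placebo = β2 + (e_i,TE2 − e_i,placebo).

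B_i, O_i and u_i cancel. Order is read here as the sequence; if it meant period, B_i would still cancel. The variance of the estimated effect is therefore σ_d²/n, with n the number of women who have both periods, and baseline does not reduce it.

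**4. Size of the loss.** With *m* of 30 women deleted, the standard error is multiplied by √(30/(30 − m)). The range of *m* is an assumption.

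| m | women left | SE ratio |
|---|---|---|
| 1 | 29 | 1.017 |
| 2 | 28 | 1.035 |
| 3 | 27 | 1.054 |
| 4 | 26 | 1.074 |
| 5 | 25 | 1.095 |
| 6 | 24 | 1.118 |

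**5. Check by simulation.** Settings: 300 replicates, 30 women, unit variances, correlation 0.5 among the baseline and the two post-treatment values, standardized effect 0.5, baseline missing completely at random. Under these settings σ_d² = 2(1 − 0.5) = 1, so theory gives 1/√30 = 0.183 for the full-data SE; the simulated mean was 0.179.

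| baselines missing | SE, women deleted | SE, baseline mean-filled | SE, baseline omitted from model |
|---|---|---|---|
| 0 | 0.179 | 0.179 | 0.180 |
| 3 | 0.191 | 0.180 | 0.180 |
| 5 | 0.195 | 0.179 | 0.179 |
| 6 | 0.200 | 0.180 | 0.181 |

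The ratio of deleted to mean-filled SE is 0.191/0.180 = 1.06, 0.195/0.179 = 1.09 and 0.200/0.180 = 1.11, in line with step 4. A second simulation of 150 runs with 4 baselines missing gave 0.194 with deletion and 0.180 with mean-filling. Mean estimates were close to the true 0.5 under every approach (0.49 to 0.52), so the issue is precision and not bias when the loss is random.

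**The case against.** The strongest reply has four parts.

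*The sentence is about drop-out.* Read with the one before it, it concerns drop-out under a missing-at-random assumption, and for that it is correct. It also says only that the analysis plan is unaffected. Both points are fair. The defect is a second source of missing data that the reasoning does not reach.

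*Section 8.1 already has mean imputation.* It does, and if applied to baseline EEG it would keep these women. But it is a sensitivity analysis with no variables named, so the primary fit still drops them. As worded it could also be applied to outcomes, which is a different matter.

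*The problem may never occur.* Section 4.3 rejects epochs, not sessions, and no failure rate is given. This stands. With one or two women affected, the standard error rises by only about 2% to 4%.

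*Baseline is not always redundant.* For a woman with only one treatment period, it helps the between-woman comparison. This also stands, and up to five withdrawals are expected.

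A reader might go further and infer that Aim 1 also loses women. Aim 1 is indeed ordinary regression ("Linear regression models will predict irritability symptoms and EEG variables from E1G variability (3) and predict irritability symptoms from EEG measures (2")), so the mixed-model argument does not apply to it. But nothing restricts Aim 1 to completers, and N = 30 in Section 9 is a planning number. A gain from analysing 35 women cannot be claimed either: Section 5.1 places the five withdrawals after randomization, whereas the synopsis and Section 5.3.2 place them after enrollment, possibly before the baseline data exist.

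A reader might also translate the loss into power from the 85% in Section 9. That figure is for irritability, whose Aim 2b model uses "fixed factors including baseline irritability symptoms (continuous), Condition, and order of Condition in a linear mixed effects model" and no EEG covariate. Section 9 states no power for the effect of estradiol on EEG.

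**Conclusion.** The point holds for the primary Aim 2a fit. As written, a woman without a usable Visit 4 EEG is removed even when both her treatment EEGs are usable, and neither 8.3 nor 8.1 prevents it. The cost is a rise of about 2% to 12% in the standard error if 1 to 6 of 30 women are affected. That range is assumed, not documented. The calculation takes both periods as observed for all 30 women and the loss of baseline as unrelated to outcome. The effect is modest, but it is avoidable at almost no cost and concerns a primary outcome. The documents do not support extending the point to Aim 1 or Aim 2b, or expressing it as a fall from 85% power.

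**What to change.** Replace the sentence in 8.3 with:

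> The mixed models use all observed post-treatment values. In the primary Aim 2a model a missing baseline EEG value is replaced by the mean of the observed baseline values pooled over both sequences, so that women with treatment EEGs are retained; outcomes are not mean-imputed in the primary analysis.

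Mean replacement is acceptable here because the covariate is measured before randomization and the filled value does not depend on sequence. Section 8.1 should then be reconciled: say which variables its complete-case and mean-imputed analyses cover, and that they are secondary to the fit above. It would help to state, before unblinding, when a baseline EEG session counts as unusable, since Section 4.3 gives no such rule.

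The cost is a few sentences of text, with no new data or participants. The one statistical downside is a slightly weaker baseline adjustment for the women whose value is filled, which matters mainly for those with only one treatment period.

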8.4. Planned Interim Analyses

We will review safety data (adverse events) continuously, however, no formal interim analyses are planned.

9. Sample Size Rationale

We will enroll 50 perimenopausal women, 45 - 59 years of age, who have high probability for affective susceptibility to *changes* in E2 by recruiting women who: 1) report the emergence of irritability concurrent with entering the menopause transition; 2) are in the early menopause transition stage; and 3) have had 1+ recent severe stressful life event. However, as described earlier, we anticipate that 30 will meet all eligibility criteria and complete the study.

Based on large effects in our prior work of ovarian hormone changes on daily symptoms of depression, anxiety, and impulsivity (average f=0.69), 31 and other studies showing strong correlations between E2 levels and EEG theta and beta power in women (f=0.79; d=1.58), 47 we expect to find large effects of E1G variability in **Aim 1**. With N = 30, we will have > 95% power to detect large effects of E1G variability on irritability symptoms (f=0.69), and we maintain 85% power to detect medium effects (f=0.25). For **Aim 2**, with N = 30, we will have over 95% power to detect large effects of TE2 on irritability symptoms consistent with the magnitude of reduction seen in irritability symptoms in a study using TE2 to treat depression (f=0.55; d=1.11). 27 With N = 30, we will maintain 85% power to detect a medium effect of TE2 on irritability (f =0.25). While we considered powering to detect small effects, detecting small effects would be unlikely to have the same degree of clinical relevance and unlikely to provide a strong scientific premise to pursue our R21 project results further.

10. Data Capture and Database Management

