5. A history of E2 dependent neoplasia **6.** A history of liver dysfunction 7. A personal or family history suggesting elevated risk for E2-related cancer or thrombotic events 8. Use of psychotropics or hormonal agents **9.** A history of psychosis or bipolar disorder **10.** Suicidality with intent **11.** Current mood disorders of severity to require treatment A total of N = 50 eligible individuals will be enrolled. Based on our prior Numbers of Enrollees studies of TE2, of the estimated 50 women who pass our phone screening and come to an in-person enrollment, we predict that 30% (n=15) will not meet eligibility for TE2 after personal and family history review or will not meet reproductive staging criteria based on further detailed questions about their menstrual bleeding patterns. We anticipate that up to an additional 15% (n =5) may withdraw after enrollment, yielding 30 women who we anticipate will complete all aspects of the protocol and will have complete data. Up to 135 individuals will be recruited and screened. 40% will fail the screening for TE2 eligibility, and an additional 20% will not be interested in participating. Using a within-subjects, cross-over, placebo-controlled, double-blind Interventions or design, participants will be randomized (1:1) to either three weeks of **Exposures/Conditions** transdermal E2 (0.1 mg/day) or to three weeks of transdermal placebo as their first condition (Condition 1). Weekly mood ratings and daily ill temper (irritability) ratings will be collected across the three weeks. In week 3 of each Condition, daily E1G collections will commence (days 15-21) and the EEG session with Dot-Probe and Affective Posner Paradigm tasks will be administered (day 21). A three-week washout period will follow. Condition 2 (3 weeks) will follow the washout (placebo E2 if Condition 1 was active E2 or active E2 if Condition 1 was placebo) with identical assessments and timeline as for Condition 1. To prevent TE2-induced endometrial hyperplasia, 200 mg micronized progesterone/day for 10 days will be given to all women at study completion (Progesterone follow-up phase). **Outcome Measures** For Aim 1. Over the four-week baseline period, irritability symptoms will be measured daily using the III temper subscale of the Inventory of Depression and Anxiety Symptoms (IDAS). Urinary measures of E1G will be collected every other day (14 samples total) and assayed using an enzyme immunoassay (Arbor Assays, Ann Arbor, MI), with sensitivity at < 22.5 pg/mL to calculate within subject fluctuation in E1G (indexed by the standard deviation of E1G over the four weeks). At the end of baseline week 4, Theta and Beta oscillatory frequencies will be assessed at rest and in response to the Dot Probe task which measures attention bias to angry faces (threat attention bias) and in response to the Affective Posner Paradigm that measures relational aggression (approach behavior) in response to frustration. For Aim 2. The outcomes are identical to those in Aim 1. The primary comparison will be within subject - comparing the active TE2 condition

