Duration of Conditions: We have chosen 3-week duration for each Condition based on: 1) The results of co-Investigator, [name], showing maximal effect of TE2 on irritability symptoms within one week; 2) placebo-controlled studies showing TE2 reduces perimenopausal depression symptoms with maximal effects seen in one to three weeks;^{27,28} 3) withdrawal from TE2 increases depressive symptoms within one week in perimenopausal women with histories of perimenopausal depression;²⁹ and 4) clinical experience that maximal efficacy of TE2 for treating perimenopausal depression is evident within two weeks (personal communication, [name]). Thus, the beneficial mood effects of TE2 are rapid and detectable within 3 weeks. With the mean half-life of TE2 equal to 161 mins,³⁰ pharmacokinetic clearance is complete in 13 hours (five half-lives). We will employ a three-week washout window to minimize, if not eliminate, even lagged carryover effects³¹

3. Specific Aims

Alignment of the	Specific Aims with Measures	and Aim-Specific Statistical A	Analysis Plans
Specific Aim	Outcome Measures	Estimands	Statistical Estimators
(1) Determine baseline relationships:			
a) E1G variability and irritability symptoms	-Every-other-day baseline E1G measurements -weekly irritability score	-Standard deviation of 14 E1G measurements -average of 4 weekly irritability (IDAS) scores	Model-based estimates, all with 95% C.I., regression coefficients
b) E1G variability and neural oscillations	-E1G standard deviation -frontal theta (dB) during threat, parietal beta (dB) during frustration	-E1G standard deviation -average event-related theta (dB) during Dot Probe Paradigm/ average event-related beta (dB) during Affective Posner Paradigm	Model-based estimates, all with 95% C.I., regression coefficients
c) irritability symptoms and neural oscillations	-weekly irritability score -frontal theta, parietal beta	-average of 4 weekly irritability scores -frontal theta (dot probe), parietal beta (Affective Posner Paradigm)	Model-based estimates, all with 95% C.I., regression coefficients

(2) Determine effect of TE2 administration on:

a) neural oscillations -Event-related frontal

-Event-related frontal - Frontal theta during dot theta and parietal beta probe/Parietal beta during Affective Posner

Paradigm

Model-based estimates, all with

95% C.I.

b) irritability symptoms

-irritability symptoms

-IDAS irritability symptoms

Model based estimates

3.1. Aim 1

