Define the baseline relationships between: (a) E1G variability and irritability symptom severity; (b) E1G variability and theta and beta oscillatory correlates of threat and frustration; (c) irritability symptoms and theta and beta oscillatory correlates of threat and frustration. The estimands of interest are the correlation coefficients between a) E1G variability (standard deviation (SD) of E1G over the four-week baseline phase) and irritability symptoms b) E1G variability (SD) and theta and beta oscillatory activation during threat and frustration tasks; and c) irritability symptoms and theta and beta oscillatory activation during threat and frustration tasks.

3.2. Aim 2

Determine whether TE2, versus placebo, will: a) beneficially modify task-evoked theta and beta oscillations (i.e., reduce theta and increase beta activation) in response to threat and frustration tasks; and b) reduce irritability symptom severity. The estimands of interest are a) the mean difference (and direction of difference) between the active TE2 and placebo TE2 conditions in theta and beta activation to threat and frustration tasks and b) the mean difference (and direction of difference) between the active TE2 and placebo TE2 conditions in mean irritability symptom severity.

4. Study Design

This single site, interventional study employs a within-subjects, cross-over, placebo-controlled, double-blind design.

Stage 1: A four-week baseline assessment involving: 1) at home urine collections of E1G; 2) mood ratings (general mood and irritability specific ratings); and 3) in-lab EEG session to assess theta and beta oscillations in response to behavioral tasks designed to elicit threat reactivity (Dot Probe task) and frustration to non-reward (Affective Posner Paradigm). Four weeks was chosen to allow for a sufficient number of E1G collections (n=14) to calculate a reliable standard deviation score for each participant.

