4.3. Measurement Design

Table 1. Variables of interest: their occasions of evaluation, their uses for the aims, their roles in the study

Variables within Domains	Scale ¹	Visits ²	Aims	Main Roles
Identifiers				
Participant ID	nominal	all	all	identifier
Screening Profile				
systolic blood pressure (SBP)	mmHg	0, 5-7, 11-13	N/A	screening and safety
diastolic blood pressure (DBP)	mmHg	0, 5-7, 11–13	N/A	screening and safety

body mass index (BMI)	kg/cm ²	0, 7, 13	N/A	screening and safety
age	decimal yrs	0	N/A	screening
Life Events Survey	binary	0	N/A	screening
Psychiatric history	categorical	0	N/A	screening
Medical and cancer history	binary	0	N/A	screening
Reproductive Stage	binary	0	all	screening
Research Lab Assays				
Urinary E1G	pg/ml	1-4, 7, 13	Aim 1	predictor
EEG (theta and beta) oscillatory activation	dB	4, 7, 13	all	primary outcome
Patient-Reported Outcomes				
Daily self-reported irritability	continuous	1 – 13	all	primary outcome
Behavioral inhibition/Activation Scale (BIS/BAS)	continuous	4, 7, 13	Aim 2	secondary outcome
Frustration to non-Reward Scale	continuous	4, 7, 13	Aim 2	secondary outcome
Green Climacteric Scale	continuous	0, 4, 7, 13	all	covariate
Pittsburgh Sleep Quality Index	continuous	0, 4, 7,13	all	covariate
Safety Monitoring				
AEs and SAEs documentation	events	0, 4-13	N/A	safety monitoring

¹Units of measurement or the scale.

Screening Measures:

Blood pressure will be taken at baseline to confirm eligibility (< 160/100 mmHg) based on a minimum of three stethoscopic blood pressures taken by a trained research staff member. Participants will be seated comfortably for a minimum of five minutes prior to the first reading with arm supported on a table. Assessments will be at least one minute apart. A mean systolic and diastolic pressure (SBP and DBP) will be derived based on the three readings. Participants must have a resting SBP <160 and a resting DBP <100 mmHg to continue in the research. The same BP protocol will be used at study visit 5-7 and 11-13 to ensure the participant remains normotensive.

Body Mass Index will be derived based on height and weight measured by a research assistant in the laboratory using the Health-o-meter (Professional) scale. BMI will be calculated using the formula: weight in kg/height in m²

Age will be determined by self-report.

Reproductive Stage will be initially determined by phone and confirmed in the enrollment session based on self-report of bleeding patterns.

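### Section 9 claims 85% power at N = 30 for a medium Aim 1 effect (f = 0.25); the planned baseline regression gives about 26%

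*Combined protocol and SAP*

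**What the plan says.** Section 9 bases Aim 1 on an expected large effect: with N = 30, "we will have > 95% power to detect large effects of E1G variability on irritability symptoms" (f = 0.69). The same sentence adds that "we maintain 85% power to detect medium effects (f=0.25"). It names no test, alpha, number of repeated measures or within-subject correlation. It gives the same 85% at f = 0.25 for the Aim 2 treatment comparison.

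The Aim 1 analysis is set out elsewhere:

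- Section 8.3: "Linear regression models will predict irritability symptoms and EEG variables from E1G variability". The mixed model with a random intercept is specified for Aim 2.
- Section 3.1: "The estimands of interest are the correlation coefficients between a) E1G variability" and irritability or EEG activation.
- Section 3 table, predictor: "Standard deviation of 14 E1G measurements". Section 8.1 agrees, specifying 14 every-other-day samples.
- Section 3 table, outcome: "average of 4 weekly irritability (IDAS) scores".

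Two places describe the inputs differently. For the outcome, the synopsis says "Over the four-week baseline period, irritability symptoms will be measured daily", and Table 1 in section 4.3 lists "Daily self-reported irritability". For the predictor, the synopsis analysis plan bases the E1G standard deviation on seven daily measurements instead of 14.

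**The concern.** A regression of one outcome value on one predictor value per woman has 30 independent observations. In a sample of that size a correlation of about 0.24 is hard to detect, and 85% is far above what such a test usually delivers. Figures of that order are typical of within-subject comparisons, where the repeated measures reduce the error term.

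Section 9 offers the 85% as assurance that N = 30 covers medium associations as well as large ones. If the true power is about 26%, a real association of f = 0.25 would give p > 0.05 about 74% of the time (1 − 0.262), where the plan implies 15%. Anyone judging what Aim 1 can show would be working from the wrong figure.

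**Working it through.** **Inputs.** N = 30, f = 0.25, f = 0.69 and the stated powers come from section 9. That f is Cohen's f follows from section 9's own pairs: 1.58/2 = 0.79, and 1.11/2 = 0.555 against the stated 0.55. So f is neither f² nor r. Two-sided alpha 0.05 is assumed; section 8.3 reports 95% confidence intervals but states a two-sided test only for Aim 2.

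**Formula.** For one predictor, the F test has 1 and N − 2 degrees of freedom and noncentrality λ = N·f². Power is the probability that this noncentral F exceeds the 5% critical value. With a random normal predictor, λ = f²·S with S distributed chi-square on N − 1 degrees of freedom, and power is averaged over S.

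**Step 1: the plan's large-effect figure.** f² = 0.69² = 0.4761 and λ = 30 × 0.4761 = 14.28. Power is 95.4% (fixed) or 92.6% (random). The stated figure of more than 95% reproduces with a fixed predictor.

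**Step 2: the plan's medium-effect figure.** f² = 0.0625, R² = 0.0625/1.0625 = 0.059, r = 0.243 and λ = 30 × 0.0625 = 1.875.

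- Fixed predictor: 26.2%.
- Random predictor: 25.5% (bivariate-normal simulation, 400,000 runs: 25.4%).
- Fisher z: atanh(0.243) × √27 = 1.286, giving 25.1%.

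The stated 85% does not reproduce.

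**Step 3: what 85% would need.** At N = 30 it needs f = 0.567 (r = 0.493, fixed) or f = 0.597 (r = 0.513, random). At f = 0.25 it needs 146 women (fixed) or 149 (random).

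**Step 4: more lenient versions of the same regression, f = 0.25.**

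| Change | Power |
|---|---|
| One-sided alpha 0.05 | 37.9% fixed, 36.8% random |
| Two-sided alpha 0.10 | 38.0% fixed |
| N = 35 | 30.1% fixed, 29.3% random |
| N = 50 (all enrolled) | 41.0% fixed |
| Two covariates explaining 30% to 50% of outcome variance, independent of E1G (assumed) | 35.9% to 48.6% |

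Covariates would have to explain about 76% of outcome variance to reach 85%. Multiplicity works the other way: a Bonferroni split over 3 to 5 tests gives 13.7% to 9.9%, and Benjamini-Hochberg lies between that and the unadjusted figure.

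**Step 5: where a figure near 85% does appear.** For a within-subject repeated-measures test, λ = f²·N·m/(1 − ρ). With m = 3 measures and ρ = 0.5 (both assumed), λ = 0.0625 × 30 × 3/0.5 = 11.25 on 2 and 58 degrees of freedom, and power is 84.1%. That calculation does not fit a baseline regression between women.

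**The case against.** **The predictor might vary within a woman.** The synopsis bases the Aim 1 standard deviation on seven daily samples, and seven daily samples are collected only in the last week of each condition. Table 1 lists urinary E1G at visits 1–4, 7 and 13 as an Aim 1 predictor. Three standard deviations per woman could therefore exist, so the documents do not support saying that E1G variability can never be a within-woman factor. But the section 3 table and sections 3.1 and 8.1 tie Aim 1 to baseline, and section 8.3 plans linear regression for it. A seven-day standard deviation would still be one value per woman in that regression.

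**The scale of f is not stated.** Section 9 takes its large effect from work on daily symptoms. If f referred to a single rating, averaging would raise the correlation to r/√[(1 + (k − 1)ρ)/k]. Four weekly ratings then give 32% to 59% (between-week correlation 0.7 to 0.2, assumed). Twenty-eight daily ratings give 34% to 70% (correlation 0.7 to 0.3, assumed) and reach 85% only at a correlation of about 0.19 to 0.21 or less. Section 9 states no such basis.

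**The consequences are limited.** Section 9 rests Aim 1 on a large effect. Section 8.1 reports large p-values as inconclusive, requires confidence intervals and disclaims reading truth or importance into a p-value. A reader might infer that null Aim 1 results will be misinterpreted; those safeguards do not support that prediction.

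**Other inferences that go too far.** One is that the figure at f = 0.69 is also wrong. Under the standard fixed-predictor calculation it is right, and the 92.6% depends on treating the predictor as random. Another is that the 85% was carried over from Aim 2. The match in Step 5 is suggestive, but section 9 gives no method.

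**Conclusion.** The 85% figure is wrong as written for the planned Aim 1 analysis. At N = 30 and f = 0.25 the baseline regression has about 26% power, a shortfall of about 59 percentage points (85 − 26). This rests on two-sided alpha 0.05, f defined on the value entering the regression, and no covariates or multiplicity adjustment. No alternative alpha, sidedness or N up to 50 that was tried exceeds 41%. Reaching 85% needs either covariates explaining about three-quarters of outcome variance or a favourable rescaling of f, neither of which is stated in section 9.

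The finding is limited to that one figure. It does not extend to the large-effect statement for Aim 1 or to either Aim 2 figure, and it does not show that the trial is too small for the effect it expects.

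**What to change.** In section 9, replace the Aim 1 85% statement with:

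> With N = 30 and two-sided alpha 0.05, unadjusted for covariates and multiplicity, power is about 26% for f = 0.25 (r = 0.24); the smallest association detectable with 85% power is about f = 0.57 to 0.60 (r about 0.49 to 0.51).

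If the sponsor intended a different alpha, test or scale for f, section 9 should state it and the figures should be recalculated on that basis. Leave the statement of more than 95% power at f = 0.69 unchanged.

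The cost is a wording change to one sentence, and one stated power figure becomes less favourable. There is no change to sample size, design or tests.
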